In Experiment 1, participants will be required to learn an upper limb precision aiming task while receiving postural support (i.e., balance facilitation) or no postural support. Baseline performance will be measured prior to a practice period. For this pre-test, participants will stand on the force platform for 30 s trials. Within the VR environment, participants will see an anteriorly placed circular target and will be instructed to maintain the position of a virtual laser pointer in the target via a handheld device in the dominant hand (or both the non-paretic and paretic hands for participants with stroke) with the upper limb held at the side. The target will change color to communicate task accuracy to participants: When the virtual laser is correctly positioned within the target, the target will be blue, but misaiming will turn the target red, indicating the need to correct the laser position. Participants will only visualize the laser and target in VR; there will not be a virtual representation of the upper limb. Participants with stroke will complete two 30 s pre-test trials with each hand (paretic and non-paretic). Postural sway and projection of the laser will be measured and recorded.

Transfer Task

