As therapists expect that training in a set of tasks might benefit performance of other similar but untrained tasks (i.e., transfer), a task to assess transfer will also be implemented. This task will be completed both prior to the practice period (to obtain a baseline level of performance for comparison after practice) and after the practice period. In the transfer task, participants will attempt to use their dominant hand (or both non-paretic hand and paretic hand for participants with stroke) second digit to produce a specified level of light touch force (0.5-1 N to prevent physical stabilization) on the force transducer. Like the laser pointer task, this task requires integration of postural control with precision manual performance (e.g., Riley et al., 1999b). Participants will receive visual feedback regarding their level of light touch force production on a visual display. A vertical bar will appear on the screen. The bar will increase in vertical size with increased force production and decrease in size with less force production. The bar will change color to reflect the level of force production. When the bar is blue, the desired level of force production has been achieved. When the bar is red, the participant needs to alter the level of force production. A horizontal line will also indicate target force production. Participants will complete two 30 s trials of the transfer task. Participants with stroke will complete the transfer trials with each limb.

Practice

Following the pre-test and baseline transfer task, participants will engage in 10, 1 min practice blocks in which they are to practice the laser task with the target positioned

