laterally. This lateral placement of the target during the practice period (as opposed to the anterior position of the pre-test) will prevent one group of participants from practicing under the exact conditions of the pre-test, which could bias the results. This will also allow for an assessment of differences in sway variability that may facilitate performance at post-test, thus providing insights about generalizability. The control group will receive no physical support to maintain balance. The experimental group will receive physical support (whether physical support is warranted or not) to minimize postural sway fluctuations. Participants with stroke will use the paretic hand. Participants will be outfitted with a gait belt, and physical support will be provided through the use of the gait belt and other traditional physical therapy guarding techniques (O'Sullivan et al., 2019). Thus, participants in this group will not be required to coordinate posture and task performance because postural stabilization will be provided externally through physical support. Postural sway and virtual laser position will be synchronously recorded during the practice period. Participants will rest for a self-selected period between each trial.

Immediate Post-Test and Retention

Participants will complete a post-test following the same procedure as the pre-test (i.e., target task). The post-test will also involve the previously described transfer task. Participants will complete two 30 s trials of each task (target/force production). Participants with stroke will complete the trials with each limb. Task and condition will be randomized. No physical support will be provided in the post-test.

Design

To evaluate the learning effect in participants with stroke, the two groups (experimental, control), two hands (paretic, non-paretic), and two test conditions (pre-test, immediate post-test) will result in a $2 \times 2 \times 2$ mixed design for Experiment 1. Participants with stroke will complete 2 trials of each test condition per limb for a total of 8 test trials per participant. To evaluate the role of therapist support during practice, each participant will complete 10 practice trials. Participants will complete 4 trials (2 trials per limb) of the transfer task before and after practice for a total of 8 trials.

Proposed Data Analysis

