Due to the wide use of COP path length and standard deviation (SD) of COP in the literature, these metrics will also be measured to further quantify changes in postural sway. These metrics are also important for assessing the distribution of sway in each plane as a function of task demand. COP path length refers to the amount of displacement of the location of the (resultant) vertical ground reaction force vector. Increased COP path length is often interpreted as reduced stability. SD of the COP is the typical method used to quantify the variability in COP trajectories. Higher values for SD of the COP indicate increased variability. COP path length is a bi-planar measure whereas SD of the COP will be calculated separately for each plane.

Supra-Postural Task Performance

Root mean square (RMS) deviation of the observed supra-postural task performance from the expected values will be used to determine the accuracy of supra-postural task performance. For Experiments 1 and 2, this will be defined as the deviation of the laser position from the target. For the transfer task, this will be defined as the deviation from the target range of light touch force production.

Statistical Analysis

To characterize learning of the practiced supra-postural laser/target task and the associated postural sway patterns, trials (error score and postural sway metrics) for both experiments will be submitted to mixed-effects models. Group (experimental, control), test condition (pre-test, immediate post-test), limb (paretic, non-paretic), and their interactions will be entered as fixed effects, and participant will be entered as a random effect. To assess performance (error score and postural sway metrics) during the practice period, trial number (1-10), group (experimental, control), and their interaction will be

entered as fixed effects and participant will be a random effect. For the transfer task (error score and postural sway metrics), group (experimental, control), test condition (pre-test, immediate post-test), limb (paretic, non-paretic), and their interactions will be entered as fixed effects, and participant will be entered as a random effect. A backward stepwise approach will be used for model building. Simple effects and pairwise comparisons will be used to follow up on significant interactions.

Relevant References

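### Half of the laser test trials come from the hand that did not practise, and backward stepwise selection can turn the learning estimate into a two-hand average

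*Combined protocol and SAP*

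**What the plan says.** - **Practice.** The plan says that "participants will engage in 10, 1 min practice blocks in which they are to practice the laser task with the target positioned" to the side. On the hand to be used it says: "Participants with stroke will use the paretic hand". No practice with the non-paretic hand is described. Under Participants, all 20 people in Experiment 1 (10 per group) have had a stroke.
- **Testing.** At pre-test, "Participants with stroke will complete two 30 s pre-test trials with each hand (paretic and non-paretic"). At post-test, "Participants with stroke will complete the trials with each limb".
- **Design.** The learning effect is to be evaluated with two groups, "two hands (paretic, non-paretic), and two test conditions (pre-test, immediate post-test"). The trial count is explicit: "Participants with stroke will complete 2 trials of each test condition per limb for a total of 8 test trials per participant".
- **Statistical Analysis.** The laser test trials go into one mixed-effects model whose purpose is given as "To characterize learning of the practiced supra-postural laser/target task and the associated postural sway patterns". Group, test condition, limb and all their interactions are fixed effects, and participant is a random effect. The force task has a model with the same terms. Models are to be built by backward stepwise selection, with simple effects and pairwise comparisons after significant interactions. No removal criterion is given, and no term is protected from removal.
- **Not stated.** The plan does not say which contrast is the learning estimate, what role the non-paretic laser trials have, or how a limb interaction will be interpreted.

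**The concern.** The trial asks whether physical support during practice changes what is learned. The most direct measure of that is the group difference in pre-to-post gain in the hand that practised. The plan does not name this quantity. It puts trials from a practised and an unpractised hand into one model and lets selection decide whether the two hands may differ in their group effect.

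Two things are at stake. First, the meaning of the reported group x test effect depends on the data: it concerns one hand if the three-way term stays, and an average of two hands if it goes. Second, the limb factor is labelled by paresis, while in every participant it also marks which hand practised. A larger gain in the paretic hand could come from either source, and the plan does not warn the reader of this.

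**Working it through.** **1. Trial count.** 2 trials x 2 test conditions x 2 hands = 8 per participant, which reproduces the figure under Design. The non-paretic share is 2 trials x 2 test conditions = 4 of 8, or 50%. Over 20 participants this is 4 x 20 = 80 of 8 x 20 = 160. The ten practice trials have their own model; if they were counted as well, the share would be 4 of 18 (22%). Here, unpractised means without practice blocks, since both hands do the pre-test trials.

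**2. Aliasing.** Let G = group, T = test, L = limb (1 = paretic) and P = practised hand (1 = yes). Everyone practises with the paretic hand, so P = L in every row and their correlation is 1.0. The planned fixed-effects matrix (20 participants x 8 trials) has 8 columns and rank 8. Adding P, P x T, P x G and P x T x G leaves the rank at 8. No analysis of this schedule can separate limb x test or group x test x limb into a paresis part and a practice part. The limb difference at pre-test precedes practice and is not affected.

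**3. What the group x test term estimates.** Let D be the group difference in gain in the practised hand and kD the difference in the other hand. The documents give no value for k, so it is an assumption. With balanced trials:

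- three-way term kept: the paretic contrast is D and the non-paretic contrast is kD;
- three-way term dropped: the group x test coefficient is (D + kD)/2 = (1 + k)/2 x D.

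Least-squares fits to the planned layout confirm this:

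| k (assumed) | group x test, term dropped | paretic contrast, term kept |
|---|---|---|
| 0 | 0.50 D | 1.00 D |
| 0.25 | 0.625 D | 1.00 D |
| 0.5 | 0.75 D | 1.00 D |
| 0.75 | 0.875 D | 1.00 D |
| 1 | 1.00 D | 1.00 D |

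**4. How easily the term could be dropped.** Assume a random intercept per participant and equal residual variance s² in both hands. The gain in one hand (mean of 2 post trials minus mean of 2 pre trials) has residual variance s²/2 + s²/2 = s². With 10 per group, the group difference in that gain has variance V = s²/10 + s²/10 = s²/5.

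- Practised-hand contrast: D/√V.
- Three-way term: (1 − k)D/√(2V), which is (1 − k)/√2 of the line above: 0.71, 0.53 and 0.35 at k = 0, 0.25 and 0.5.
- Two-hand average: [(1 + k)/2]D/√(V/2), which is (1 + k)/√2 of the first line. This exceeds 1 when k > √2 − 1, about 0.41.

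The term that protects the practised-hand estimate is therefore tested with less power than that estimate itself. A non-significant three-way term is weak evidence that the two hands respond alike.

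**The case against.** The strongest reply is that the randomised comparison is sound. Both groups practise with the same hand and are tested with both, so group x test within either hand is a valid contrast. The planned full model includes the three-way term and recovers the practised-hand effect. In the plan's wording, practised describes the task and not the hand. Several outcomes are whole-body sway measures, and nothing in the documents says that the learning is specific to one hand. Testing both hands is thus a reasonable choice. All of this stands.

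Three stronger readings are tempting, and the documents do not support them:

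- A reader might infer that the plan will interpret limb effects as effects of paresis. No section states such a hypothesis or conclusion. The gap is a missing caveat, not a contradiction.
- A reader might infer that the learning effect is diluted by up to half as planned. That happens only if the three-way term is removed or a pooled effect is reported, and its size depends on an assumed k.
- A reader might infer that the non-paretic laser trials have been left out of every outcome. They are in the learning model; what is missing is a statement of what they measure there. Nor do they fall under the plan's own use of transfer, which concerns untrained tasks.

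What remains after these concessions is the stepwise rule: it leaves open whether the reported learning effect belongs to one hand or two.

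**Conclusion.** The point holds in a limited form. Half of the trials in the laser learning model come from the hand without practice, and limb and practice status are identical in all 20 participants. No bias follows in the within-hand randomised contrasts or in the full model. The exposure comes from backward selection: if group x test x limb is removed, the reported effect is (1 + k)/2 of the practised-hand effect, or 0.50, 0.63 and 0.75 at k = 0, 0.25 and 0.5. Separately, neither limb x test nor the three-way term can support a statement about paresis. The same holds for the force-task model, because both limbs are tested there after paretic-only practice.

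This rests on the assumed values of k and on reading the paretic-hand sentence as covering both groups. It follows the description of the experimental group but is worded for all participants with stroke, and everyone in Experiment 1 is one. If it covered only one group, the practised hand would be undefined for controls. The point is worth acting on because the remedy is cheap, but it does not invalidate the design.

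**What to change.** In Statistical Analysis:

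- Keep group x test x limb (and its lower-order terms) in the laser model whatever the stepwise procedure indicates.
- Pre-specify the group x test contrast in the practised (paretic) hand as the learning estimate.
- Report the same contrast in the unpractised (non-paretic) hand separately, as inter-limb carry-over.
- State, for both the laser and the force-task models, that limb x test and three-way terms after paretic-only practice do not support a conclusion about paresis.

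In Practice, make explicit that the statement on the hand used applies to both groups.

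The change is to wording only and adds no trials or participants. Its cost is that the learning estimate rests on half of the test trials per participant (4 of 8). Under a random-intercept model with equal residual variance, it is less precise relative to its effect than pooling once k exceeds about 0.41. Pooling would then estimate the two-hand average, which is a different quantity.

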**The Motor Control Consequences of Excessive Physical Therapist Support in
Individuals with Stroke (NCT04856527)**

University of Cincinnati IRB Protocol 2020-1072

Most recent IRB approval: 2021-10-07

STUDY PROTOCOL AND STATISTICAL ANALYSIS PLAN

Study Protocol

Participants

Twenty participants aged 21-85 years¹ previously diagnosed with stroke (>1-month prior to enrollment to ensure medical neurologic stability) will participate in Experiment 1 (10 participants in experimental group, 10 participants in control group). Participants will be randomly assigned to a group. Participants must demonstrate independence or modified independence during ambulation (defined as the ability to ambulate with no physical assistance and use an assistive device as needed). Participants must score 0-3 on the Modified Rankin Scale (de Haan et al., 1995; Rankin, 1957), which indicates complete independence to moderate disability but able to walk without assistance. Participants must be able to maintain standing balance for >2 minutes with no physical support and maintain grasp of a handheld object with at least one hand. Participants are permitted to be active in programs of physical therapy or occupational therapy at the time of enrollment. All gender identities and all races/ethnicities will be eligible for participation.

Participants with stroke will be excluded due to limited language/cognitive abilities, deafness, blindness, or serious motor impairment that outright prevents performance of the experimental tasks (e.g., severe upper or lower extremity spasticity). Participants will be excluded if they are pregnant. Participants will also be excluded if they experience pain with weightbearing >4/10. Participants will complete the Mini Mental State Exam (Folstein et al., 1975) prior to study start to ensure cognitive capacity to engage in and consent to the study. Participants will be excluded if they have any other medical condition that would preclude the valid administration of the study measures, specifically seizure disorders, additional neurologic conditions beyond stroke, or significant musculoskeletal conditions (e.g., lower limb amputation).

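### Task order is stated as randomised for the post-test only; if the pre-test order is fixed, pre-post change carries an order effect, though the group × test contrast stays unbiased

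*Combined protocol and SAP*

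**What the plan says.** Under Participants, the plan sets "10 participants in experimental group, 10 participants in control group" and states "Participants will be randomly assigned to a group".

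The pre-practice procedures are described under Pre-Test (laser task) and then under Transfer Task (light-touch force). The Practice section begins "Following the pre-test and baseline transfer task, participants will engage in 10, 1 min practice blocks". No sentence before practice randomises the order of the two tasks, and none fixes it.

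Under Immediate Post-Test and Retention, the plan says "Participants will complete a post-test following the same procedure as the pre-test", naming the target task, and adds the transfer task. It then says "Task and condition will be randomized". The unit of that randomisation (participant, block or trial) is not given, and neither is any balancing within group. *Condition* is not defined there. Under Design, the test conditions are pre-test and immediate post-test, which cannot be put in random order, so limb may be meant.

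Under Statistical Analysis, the laser and transfer models have the same terms: group, test condition, "limb (paretic, non-paretic), and their interactions will be entered as fixed effects", with participant as a random effect. Neither has a term for task or limb order. Models are reduced by a backward stepwise approach.

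**The concern.** Read in the order of the text, every participant does laser then transfer before practice, while after practice about half do transfer first. The two tests would then differ in task order as well as in practice. Any warm-up or fatigue effect of coming second would be part of the measured pre-post change.

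The Design section presents Experiment 1 as evaluating the learning effect, so pre-post change is itself a target. Backward elimination adds to this. If group × test is dropped, which is plausible with 10 per group, the test-condition main effect is left as the learning result, and that term would carry the order effect. So would the pre-post simple effects within each group.

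The laser task could only move from first to second, and the transfer task only from second to first. An order effect common to both tasks would therefore push their changes apart and blur the comparison of trained with transfer performance.

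**Working it through.** **Inputs from the plan.** There are 10 participants per group, 20 in all (Participants). Each task has 2 trials × 2 limbs × 2 tests = 8 test trials per participant (Design). These counts reproduce. The sample size itself cannot be reproduced, because no alpha, power, effect size or SD is given.

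**Assumptions.**
- δ is the effect of doing a task second rather than first, in SDs of the participant-level change score without any order effect. The documents give no value, so a range is shown.
- Trials are averaged to one change score per participant, which simplifies the planned mixed model.
- Alpha is two-sided 0.05. The benchmark group difference is d = 1.32, chosen because it gives 80% power with 10 per group (noncentral t, 18 df) when δ = 0.

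**Reading A: pre-test order fixed, post-test order drawn 50:50 once per participant.**
- Expected shift in pre-post change, the same in both groups: δ/2, upward for one task and downward for the other.
- Expected shift in group × test: δ/2 − δ/2 = 0.
- Added variance of change: 0.5 × 0.5 × δ² = δ²/4, so the SD is multiplied by √(1 + δ²/4).
- Effective n per group: 10/(1 + δ²/4).

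| δ (assumed) | Shift in pre-post change | SD factor | Effective n per group | Power for group × test at d = 1.32 |
|---|---|---|---|---|
| 0.2 | 0.10 | 1.005 | 9.9 | 79.6% |
| 0.3 | 0.15 | 1.011 | 9.8 | 79.1% |
| 0.5 | 0.25 | 1.031 | 9.4 | 77.6% |
| 0.8 | 0.40 | 1.077 | 8.6 | 73.9% |
| 1.0 | 0.50 | 1.118 | 8.0 | 70.8% |

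At δ = 0.5, the standard error of the group contrast goes from √(2/10) = 0.447 to 0.447 × 1.031 = 0.461 SD, about 3%.

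**Chance imbalance.** With two independent Binomial(10, 0.5) counts, the groups differ by at least 3 participants in post-test order with probability 0.263, and by at least 4 with probability 0.115. At δ = 0.5 this contributes an error with SD √(2 × 0.0625/10) = 0.11. It is the same noise as above: √(0.447² + 0.11²) = 0.46.

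**Simulation check of Reading A (20,000 trials per δ).** Type I error for group × test was 4.9% to 5.0% at δ of 0, 0.5 and 1.0. With no true learning, the pooled pre-post effect was falsely significant in about 18% of trials at δ = 0.5 and 48% at δ = 1.0.

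**Reading B: order drawn separately at each test.** The expected shift is 0. The order contribution to change is the difference of two draws, so the added variance is (0.25 + 0.25) × δ² = δ²/2. At δ = 0.5 the SD factor is √1.125 = 1.06. There is no bias, but there is more noise than under Reading A.

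**Same order at both tests.** For an order effect that is additive and equal at the two tests, the contribution to change is δ − δ or 0 − 0. The shift is 0 and the SD factor is 1.

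**The case against.** The strongest objection is that the fixed pre-test order is not in the plan. A protocol has to describe one task before the other. The phrase "Following the pre-test and baseline transfer task" lists what comes before practice without ranking the two items, and "Participants will complete a post-test following the same procedure as the pre-test" leaves room for a single order scheme at both tests. This stands. A reader might infer that transfer-before-laser never occurs at pre-test, but the documents do not say so, and the expected shift depends on that reading.

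A second objection is that the trial asks whether therapist support changes learning. That is the group × test contrast between randomised groups sharing one order scheme. This also stands. A reader might infer that the between-group result is biased; it is not, in expectation. Nor should the imbalance probabilities be counted as a problem on top of the lost precision, since they describe the same noise.

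Third, both groups practise and there is no unpractised comparator, so pooled pre-post change already mixes learning with retesting and fatigue. That is true and limits what is at stake, but it is no reason to add a further, avoidable component.

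Fourth, randomising task order is an accepted safeguard, the size of δ is assumed, and trial-by-trial randomisation would add less noise than one draw per participant. All fair. What remains is that the text supports at least two order schemes, neither ensures that a participant has the same order at both tests, and matching the orders costs almost nothing.

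**Conclusion.** The point holds as a minor design improvement, with an ambiguity to resolve. Randomised task order is stated for the post-test only, and the pre-test order is unstated.

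If the pre-test order is fixed, pre-post change shifts by δ/2 in both groups: 0.15 to 0.40 SD for assumed δ of 0.3 to 0.8 SD, in opposite directions for laser and transfer. The affected results are the test-condition main effect and the within-group simple effects. If order is drawn separately at each test, no shift is expected and only noise remains.

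Under Reading A, the group × test contrast stays unbiased and loses little: about 3% in standard error, and power from about 80% to 78%, at an assumed δ of 0.5 SD. These sizes rest on an assumed order effect, one draw per participant, and one averaged change score per participant. The documents do not support a claim that the comparison of support with no support is invalid.

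**What to change.** Draw one task and limb order per participant, balanced 5:5 for task order within each group of 10, and use that same order at pre-test and post-test. Replace the sentence "Task and condition will be randomized" with that rule, state the pre-test order explicitly, and say whether *condition* means limb.

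Matching removes the shift and the added noise under either reading, provided the order effect is additive and the same at both tests. If it differs after practice, the 5:5 balance keeps what remains equal in the two groups.

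No order term is needed in the models once orders are matched. If they are not matched, a pre-specified order term kept out of backward elimination is the alternative, but it is not free. Simulated power with and without it is about 77% versus 80% at δ = 0, 77% either way at δ = 0.5, and 77% versus 71% at δ = 1.0.

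The cost is a revised order sheet and a reworded sentence, with no added trials or participants.

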All data processing and analyses will be completed using custom R scripts (v.4.0.3). All postural sway data (i.e., center of pressure—COP) will be filtered through a 4th-order lowpass zero-lag Butterworth filter with a cut-off frequency of 6 Hz prior to analysis.

Recurrence Quantification Analysis (RQA)

RQA (Webber & Zbilut, 2005) will be used to assess the regularity of postural sway. RQA quantifies the patterning, non-stationarity, and complexity of biological time series through the analysis of local recurrences in a reconstructed phase space (Riley et al., 1999a). Recurrence plots (RPs) provide a visualization of patterns of recurrence, where a single point on the RP indicates a recurrence and a line indicates continuing recurrence (Coco & Dale, 2014). A variety of metrics are used to quantify these patterns. Percent determinism (%DET) is the percentage of recurrent points which fall on diagonal lines

and reflects how often the system repeats the same sequence of points. Thus, higher %DET is indicative of a system with more regularity. Maximum line length (MAXLINE) is the length of the longest diagonal line segment on the RP, indicating the maximum duration of time that the system is revisiting an area of reconstructed phase space. Mean line length (MEANLINE) is the average length of diagonal line segments on the RP, indicating the average duration of time that the system is revisiting an area of phase space. In the context of the current study, reduced task-sensitive adjustments (i.e., modulation in task relevant direction) in %DET, MAXLINE, and MEANLINE of postural sway (hypothesized to exist following constraining posture/task) would indicate a more regular postural control system—one that is prone to repeating the same behaviors. RQA metrics will be calculated separately for each plane.

Sample Entropy (SampEn)

SampEn (Richman, Lake, & Moorman, 2004) will be used to evaluate changes in the predictability of postural sway as a convergent measure to complement RQA. SampEn evaluates the predictability of the next state of a system, given what is known about the current state of a system (Yentes, 2016). SampEn has been widely used to assess the regularity of postural control across a variety of task conditions and populations (e.g., Schmit et al., 2016). SampEn will be calculated separately for each plane.

Traditional Analyses

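### Does the RQA hypothesis need a named task-relevant plane and a planned between-plane test?

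*Combined protocol and SAP*

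**What the plan says.** The RQA section interprets "reduced task-sensitive adjustments (i.e., modulation in task relevant direction) in %DET, MAXLINE, and MEANLINE of postural sway" as a sign of greater regularity, using the words "hypothesized to exist following constraining posture/task) would indicate a more regular postural control system". It ties %DET to regularity: "Thus, higher %DET is indicative of a system with more regularity". It then states that "RQA metrics will be calculated separately for each plane". The Sample Entropy section does the same for SampEn. Traditional Analyses computes SD of COP by plane and says of path length and SD: "These metrics are also important for assessing the distribution of sway in each plane as a function of task demand".

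The target is anterior in Pre-Test, and the post-test repeats that procedure. It is lateral in Practice. The Transfer Task section describes a light finger force and gives no direction.

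Statistical Analysis submits the error score and the postural sway metrics to mixed models. For the laser test the terms are: "Group (experimental, control), test condition (pre-test, immediate post-test), limb (paretic, non-paretic), and their interactions will be entered as fixed effects". The transfer model uses the same list. The practice model uses "trial number (1-10), group (experimental, control), and their interaction will be" entered as fixed effects. Participant is the random effect throughout, and "A backward stepwise approach will be used for model building". Plane appears in none of the lists.

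**The concern.** The hypothesis refers to a direction, yet the plan never says which plane that is for any of the three tasks. Nor is it self-evident. For a laser aimed at an anterior target, forward-backward translation runs along the beam and sideways translation runs across it, so the target's position and the pointing geometry can suggest different planes. Moving the target to the side for practice may change the answer, and the force task gives no clue.

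Two things would be at stake. If the plane were settled after the results were known, each metric would have two chances of reaching significance. If significance in one plane and not the other were then read as a direction-specific effect, no planned analysis would support that reading, because a difference in significance is not a test of a difference. The remark about the distribution of sway across planes adds to the impression that a comparison of planes was intended and left out of the models.

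**Working it through.** **Inputs.** From the documents: 10 participants per group (Participants); three RQA metrics, each computed per plane. Taken as two planes, that is 3 × 2 = 6 outcomes. The plan gives no alpha, effect size, SD or between-plane correlation, so there is no stated figure to reproduce. Assumed: two-sided alpha 0.05; a t-test on each participant's pre-to-post change (df = 10 + 10 − 2 = 18); effect d in SDs of change; between-plane correlation r. Simulated figures use 200,000 runs per setting.

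**Step 1: what the planned models test.** Each sway metric computed in a plane is an outcome in its own right. Fitting the listed effects to each gives a group by test condition term within each plane. That term answers whether supported practice changed regularity in that plane. It does not answer whether the change differed between planes. The RQA section predicts the former and nowhere asserts the latter.

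**Step 2: plane chosen afterwards, no true effect.** With independent planes, P(at least one significant) = 1 − 0.95² = 9.75%. Simulated: 9.1% at r = 0.5 and 8.4% at r = 0.7. The reference with one fixed plane is 5%. The plan does give an expected direction (more regular with support). Counting only results in that direction, the rates are 4.9%, 4.6% and 4.2%, against 2.5%.

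**Step 3: equal true effects in both planes, one chosen plane alone significant.** With r = 0 this is power × (1 − power).

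| d | power per plane | r = 0 | r = 0.5 | r = 0.7 |
|---|---|---|---|---|
| 0.5 | 0.185 | 0.185 × 0.815 = 15% | 11% | 9% |
| 0.8 | 0.40 | 0.40 × 0.60 = 24% | 17% | 13% |
| 1.0 | 0.56 | 0.56 × 0.44 = 25% | 17% | 13% |
| 1.2 | 0.72 | 0.72 × 0.28 = 20% | 14% | 11% |

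These are error rates of an informal inference that the plan does not propose.

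**Step 4: what a between-plane contrast would add.** It holds its level (about 5% in simulation). Suppose the effect is in one plane only. The standardised contrast is then d / √(2(1 − r)), and power from the noncentral t with 18 df is:

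| d | r = 0 | r = 0.5 | r = 0.7 |
|---|---|---|---|
| 0.5 | 12% | 19% | 28% |
| 0.8 | 22% | 40% | 59% |
| 1.0 | 32% | 56% | 78% |
| 1.2 | 44% | 72% | 91% |

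The 95% half-width is 2.101 × √(2(1 − r)) × √(1/10 + 1/10). This gives 1.33, 0.94 and 0.73 single-plane SDs of change at r = 0, 0.5 and 0.7.

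**Step 5: scale.** Take assumed SDs of COP of 5 mm and 3 mm, rising 20% in controls and 5% with support in both planes. The raw group differences are 5 × 0.15 = 0.75 mm and 3 × 0.15 = 0.45 mm, which look plane-specific. On the log scale the difference is ln(1.20/1.05) = 0.134 in both. So the contrast's answer can depend on the scale.

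**Step 6: does naming the plane secure 5%?** Only for one metric under a valid test. Three independent RQA metrics in one named plane would still give 1 − 0.95³ = 14.3% (six outcomes: 1 − 0.95⁶ = 26.5%). If the models carry a random intercept only, the within-plane test rejects in 4.7%, 9.7%, 14.1% and 19.9% of null trials when the between-participant SD of change is 0, 0.5, 0.71 and 1.0 times the trial SD (assumed values). A between-plane difference model behaves the same way: 5.1%, 10.1%, 14.0% and 20.3%. These are general properties of the modelling plan and do not turn on plane.

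**The case for a change.** The strongest contrary case is that a hypothesis which depends on a direction should define it, at a cost of a few sentences and no new data. The target's position does not settle the plane, so two careful analysts could choose differently. With planes modelled separately and backward elimination applied to each, the interaction could survive in one plane and drop out in the other, inviting a specificity reading with nothing behind it. A single prespecified contrast would guard against that, and its low power could be met by reporting an interval.

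Part of this stands. The term is undefined, no model contains plane, and one significant plane out of two would not show a direction-specific effect. But the definition would only record something that becomes visible anyway, since the plan has the metrics calculated in each plane and sends the sway metrics to the models. The contrast would serve a claim the plan does not make. It would not meet the remark on sway distribution either: that sentence gives a reason for using path length and SD, and its reference to task demand points to comparisons between tasks or target positions, which a group by test condition contrast within one task does not provide.

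**Conclusion.** No change to the plan follows. The wording gap is real and small: one undefined term, in a study of 20 people, whose natural per-plane analysis tests a within-plane prediction. The plan's expectation about regularity can be read directly as more stereotyped sway after support, so it needs no further statement about which way normal adjustment moves the metrics.

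The sizes, 8.4-9.8% against 5% for a plane picked afterwards and about 9-25% for a false appearance of specificity, are conditional on choosing the plane from the results or comparing significance between planes. The plan states neither. They also rest wholly on assumed alpha, effect sizes (0.5-1.2 SD) and correlations (0-0.7). A between-plane contrast would be scale-dependent and mostly inconclusive unless the planes are strongly correlated and the effect is large. The conclusion assumes that results are reported for both planes and that no claim of an effect confined to one plane is drawn from the per-plane models. A report that made such a claim would be open to criticism on its own terms.
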